1.0 PROJECT SUMMARY

Frailty is a comprehensive measure of health status that describes the vulnerability of a person to health stressors (1–4). Frailty is measured along a continuum from '*managing well*' to '*severely frail*', and is characterized by progressive impairment in activities of daily living (4). More than one out of every four patients with Chronic Obstructive Pulmonary Disease (COPD) are frail, and frailty is associated with frequent exacerbations, hospital readmission, mortality, and poor quality of life (3,5–10). Further, intervening with specialized exercise, nutritional, and personal supportive care programs has the potential to reverse, or stabilize frailty when identified at the earlier stages (2,3,7).

However, little is known about whether frailty measurements can be used to predict the risk of deteriorations in validated patient-reported outcomes, if frailty measurements are reproducible among patients with COPD, and if patient care preferences differ between degrees of frailty. Further, it is unknown whether frailty categories could be used to guide tailored interventions to address and manage frailty, and whether frailty-focused interventions could improve long term outcomes in addition to conventional treatments (6,10).

We hypothesize that progressive degrees of frailty will reliably predict important deteriorations in patient-centered outcomes over time, including health-related quality of life, symptom burden, psychosocial wellbeing, and measures of survival and health service use.

If this association between frailty and health is confirmed, then it follows that frailty could be used as a risk stratification tool to guide tailored interventions for population subgroups with varying degrees of frailty.

To inform the development and testing of effective care interventions within categories of frailty, the following questions must first be addressed:(1) What is the predictive value of progressive degrees of frailty on deterioration in patient-centered outcomes and increased health care utilization among people with COPD? (2) What are the differences in expectations of clinical care between patients and physicians within different degrees of frailty? (3) What is the inter-rater agreement between patients and physicians who use the Clinical Frailty Scale (CFS) to measure frailty? (4) What is the test-retest reliability of the CFS when used by the same patient at 2 different time-points, 6 months apart?

2.0 BACKGROUND

What is the Problem to be Addressed? Patients with Chronic Obstructive Pulmonary Disease (COPD) feel that their needs are not met within the current healthcare system (11). In a scoping review of a decade's worth of qualitative evidence, patients with COPD reported feeling poorly informed about their condition, vulnerable when hospitalized, unconfident in community based services, and lacked an understanding of their disease

trajectory and significance of their exacerbations (11). Most importantly, patients reported that their subjective distress seemed *invisible* to clinicians who tended to focus on objective health indicators, and that clinicians infrequently addressed or referred patients for assistance with their substantial non-medical needs (7).

From a health system perspective, COPD exacerbations are a leading cause of hospitalizations and re-admissions in Canada, and cost our health system over 700 million dollars annually (12,13). In a closer review of hospital-related costs for COPD care, the highest costs were incurred by patients with acute illness, but also by *frail* patients who developed significant functional limitations and could not return home (14).

Both the patient and health system perspectives suggest that our current paradigm for COPD care in Canada is not optimal. While health providers focus on COPD-specific metrics, which have been correlated with future risk of mortality and hospitalization (15–17), clinicians lack appropriate evidence based tools to evaluate the non-pulmonary complications of COPD and overall wellbeing of these patients (18).

In this setting, there is a need for innovative care approaches which (1) reliably predict the outcomes that are important to patients living with COPD, (2) are easily implemented in the health system, and (3) have a direct impact on front line COPD management across health care settings. Care models which incorporate assessments of '*Frailty*' may provide this desired innovative approach to enhance patient-centered COPD care. There are currently no studies to determine whether health providers could use measurements of frailty to accurately predict current and future decline in patient-centered outcomes, and whether patients' expectations of healthcare change between different degrees of frailty.

The aim of this research program is to validate *frailty* measurements as a risk stratification tool to predict deteriorations in patient-reported outcomes, to gain a better understanding of patient preferences for care within varying degrees of frailty, and to assess differences in frailty measurement between patients and their care team.

This work will provide a foundation in the development of customized interventions for people with COPD and varying degrees of frailty, with the goal of improving quality of life and optimizing health system service delivery for patients and their care givers.

What is Frailty and Why is it a Relevant Health Measure? Frailty is a common and important multi-dimensional syndrome characterized by a loss of reserve in multiple domains including physical ability, energy, cognition, and health (4). Loss of reserve in the frail patient leads to an increased vulnerability to adverse health outcomes such as hospitalization and death (1,4,19). As frailty progresses, the ability to recover from

both chronic and acute health stressors becomes more difficult, and leads to progressive functional disability (19).

More than half of patients over 85 years of age are identified as frail (1). However, age alone does not account for functional decline (20). The frailty construct offers a comprehensive approach to identify patients at risk of decline who would benefit from additional resources in order to address their needs. For example, frail people have been found to benefit from exercise programs to reduce falls, nutritional interventions, cognitive assessment and support, and mobility and balance training (21).

Frailty has also been identified as an important prognostic tool in patients with other chronic diseases such as heart and kidney disease (22,23). Experts hypothesize that using frailty assessments may help clarify which interventions and treatments can benefit or harm patients, help to refine clinical decisions, improve prognostication, and enhance informed decision making (24–26).

For healthcare providers, recognition of frailty in patients is crucial to facilitate identification of patients at high risk of poor health outcomes such as progressive disability, hospitalization and death (2).

Why is Frailty Relevant to COPD Care, and Why is it not Currently Used in Patient Evaluation? The prevalence of frailty among people with COPD ranges widely from 16-75%, depending on the population studied, and the frailty measurement tool used (3). In our own prospective assessment of 50 hospitalized patients with COPD exacerbation, 54% were found to be at least mildly frail at their baseline, two weeks prior to their hospitalization (27).

Studies demonstrate that people with COPD have a two-fold increase in the prevalence of frailty compared to patients without COPD, after adjustment for confounding factors including age, smoking, steroid use, and comorbidities (6). Presence of frailty is also correlated with COPD-specific markers, including severe airflow obstruction, shortness of breath, and frequent exacerbations (6). Among people with COPD, frailty is associated with increased risk of death, poor recovery after hospitalization, and re-admission to hospital (5,6,8). Emerging evidence suggests that higher degrees of frailty are also associated with poorer acceptance of illness, which may have significant implications for adherence to treatment and self-management (28).

Traditional care discussions of treatment and prognosis between patients and physicians often center around the current COPD guidelines, which focus on disease-specific metrics (i.e. lung function and exacerbation history) (16,29). While these metrics are important, one of the limitations of this approach is that it overlooks clinically relevant complications of COPD, such as co-morbidities, reduced functional capacity, and psychological well-being. These factors contribute to poor quality of life and clinical outcomes and are equally important to address (30). Frailty measurements could complement disease specific metrics when evaluating

patients and could influence care in a way that FEV1 measurements do not; however, we lack the research studies to support this hypothesis.

Given the association between frailty and poor outcomes among patients with COPD, an understanding and early recognition of frailty by health providers *and* patients could determine the choice and timing of interventions, and improve the long term clinical response (3,7).

How is Frailty Measured? There are multiple validated tools that can assess and quantify the degree of frailty in a patient (31). The Clinical Frailty Scale (CFS) is a bedside clinical tool that is easy to use, freely available, validated in the Canadian population, and correlates with objective clinical outcomes of death and need for long term care (**Figure 1**) (4). The CFS is also validated for use by patients to self-report frailty (32). Although there are no direct comparisons between frailty tools in the COPD population, among patients with cirrhosis, the CFS had greater discriminatory power for outcomes in comparison with the Fried Criteria, and Short Physical Performance Battery Scale (33).

The CFS uses an ordinal scale from '1' to '9' to characterize degrees of frailty from 'managing well' to 'terminally ill'. Each degree of frailty is accompanied by a description of physical symptoms and functional ability to perform instrumental activities of daily living (IADL's) and activities of daily living (ADL's). Although there is a degree of subjectivity in assigning a score, increasing degrees of frailty are objectively associated with increased risk of death and need for long term care in adult patients over 65 years of age (4).

Why is it Important for Patients and their Providers to have a Mutual Understanding of Frailty? There is rightfully a heightened focus on patient-centered care in our health system (34). Patient-centered care refers to the active collaboration and shared decision-making between patients, families and health providers to create and implement a personal comprehensive care plan (34). To operationalize this, patients must also have a sound understanding of their disease, prognosis and care needs.

Poor recognition of frailty or discordance between patient and healthcare providers' frailty assessments, may impact patient-centered care.

If a patient under-perceives their degree of frailty, they may not agree with or adhere to the prescribed treatment plans; for example, recognizing the need for pulmonary rehabilitation, home care services, or dialogue regarding symptom management and end of life care. If the healthcare team underperceives a patient's frailty, this can lead to delays in requesting additional resources, and possible over treatment with more invasive therapies that may not benefit a very frail patient. A discordance between patients and their healthcare providers may be a factor which contributes to the increased dissatisfaction and fragmentation of care, that is voiced by patients with COPD (11).

3.0 OBJECTIVES

The aim of this research program is to evaluate *frailty* measurements as a risk stratification tool to predict deteriorations in patient-reported outcomes, to gain a better understanding of patient and physician preferences for care within varying degrees of frailty, and to assess the change of frailty measurements over time. More specifically, our study objectives are:

1. To determine the predictive value of progressive degrees of frailty on deterioration in patient-centered outcomes and increased health care utilization among people with COPD, after adjustment for important clinical factors including age, sex, comorbidity, home support, number of medications, pulmonary rehabilitation, lung function, dyspnea, and exacerbation history.
2. To describe the differences in expectations of clinical care between physicians and patients within different degrees of frailty.
3. Determine the inter-rater agreement between patients and physicians who use the Clinical Frailty Scale (CFS) to measure frailty.

4.0 Investigate the change in frailty scores over 12 months **HYPOTHESIS**

We hypothesize that progressive degrees of frailty will reliably predict important deteriorations in patient-centered outcomes over time, including health-related quality of life, symptom burden, and psychosocial well-being, and measures of survival and health service use. If this association between frailty and health is confirmed, then it follows that frailty could be used as a risk stratification tool to guide tailored interventions for population subgroups with varying degrees of frailty.

5.0 METHODS

5.1 Design & Setting: A prospective cohort study at The Ottawa Hospital (TOH) over two years. TOH is a quaternary care academic hospital with an ambulatory care respiratory clinic, staffed by seven respirologists. It is a regional referral center with a catchment area of approximately 1 million individuals.

5.2 Study population and Inclusion Criteria: We will include literate English or French-speaking outpatients with COPD, objectively confirmed by lung function testing¹. In patients with multiple respiratory conditions and comorbidities, COPD will be the primary diagnosis, as confirmed by the treating respirologist. Participants will be recruited from the respirology ambulatory care clinics at TOH. We will exclude patients with a known diagnosis of severe cognitive impairment², if the

¹ post-bronchodilator Forced Expiratory Volume in 1 second / Forced Vital Capacity ratio below the lower limit of normal, and >10 pack years history of tobacco smoking

² as per the medical record

recruiting physician feels the impairment would preclude participation in the study.

5.3 Study flow: Prior to the clinic, members of the study team (PI and coordinator) will review the list of patients scheduled for a routine visit in the Respirology clinic of TOH during the study period. Patients who have a diagnosis of COPD will be flagged as “identified” in EPIC for the study. The name (first and last) and MRN will be included in a Master List. This list will link patients’ identifiable information (MRN and name) with a screen ID. The screen ID will be included in an *“appointment note”* within the physician’s schedule in EPIC, flagging the care team that the patient is possibly eligible for the study.

[figure not shown]
During their routine visit with respirologist in the Respirology outpatient clinic of TOH, patients will be assessed for eligibility. Prior to meeting with the respirologist, the nurse will complete their standard patient assessment. They will review the posted note left by the research team for that specific patient and assess the patient for eligibility. If eligible, the nurse will ask the patient if they agree to have a member of the study team approach them about the study. If the patient agrees to be contacted, the physician would assess patients’ frailty using the CFS, include the frailty rating and their care expectations for the patient in a form (see [Recruitment Survey](#)), with the screen ID, provided in the *appointment note*. This form would be automatically available to the research team, which would allow them to contact the patient to obtain verbal consent (see [Verbal Consent](#)) and schedule a baseline study visit. Please note, once the patient has been assessed for eligibility, the screen ID becomes the study ID for that patient.

Consent: The study team will call the patient to obtain verbal consent. If the patient agrees, the study team will schedule a baseline visit by phone with a member of the study team. Once consented, the study team will request an e-mail address to send the baseline electronic survey (see [Patient Baseline Survey](#)) and the informed consent document for additional information on the study.

Baseline visit: Prior to each scheduled visit, the baseline survey will be e-mailed to the patient with a reminder of their upcoming appointment with a member of the study team. For those who do not have or have not provided an e-mail address, a member of the team will call the patient to remind them of their upcoming appointment. During the telephone baseline visit, patients will be asked questions on their lung health (see [Data Collection Sheet – Baseline Visit](#)). If the electronic

Baseline Survey was not completed, the study team will go through the questions with the patient. At the end of the visit, the study team will schedule the 6-month telephone visits and ask the patient to confirm their mailing address to send the first of three gift coffee cards (of 20\$), as a token of appreciation.

6-month and 12-month follow-up visits: Prior to the scheduled 6-month or 12-month follow-up visit, the study team will send an e-mail to patient with a link to [the COPD & Frailty – 6-month follow-up survey](#) or [COPD & Frailty – 12-month follow-up survey](#). Patients who did not provide an e-mail address will receive an appointment reminder call from a member of the study team and complete the survey with the study team during their 6 and 12-months telephone follow-up visits. At the end of each telephone visit, patients will be asked to confirm their mailing address to send the second and third gift cards (of 20\$).

5.4 Sample Size: Sample size calculations were performed based on the primary analysis strategy, which uses multiple variable linear regression with a fixed model. We will determine the adjusted association between frailty (categorized in 4 groups using the CFS: ‘vulnerable’, ‘mildly frail’, ‘moderately frail’ and ‘severely/very severely frail’) and respiratory health-related quality of life as measured by the validated SGRQ-C, scored from 1-100. The minimally important clinical difference (MCID) for the SGRQ-C is 4 (41). We will adjust the model for confounding variables including age, sex, dyspnea severity (mMRC), hospitalization, lung function, home support services, and comorbidity scores.

In a previous sample of patients with COPD, the standard deviation of SGRQ scores ranged from 13 to 18 (9,42–44). To detect an effect size of 0.2 to 0.3, with 10 predictors and α error 0.05 and power 0.80 (1- β error), we require a range between 64 to 84 individuals (G*Power 3.1.9.2).

Copyright (C) 1992-2014, see **Appendix 1**.

Further, Harrell suggested that **10 subjects per variable** is the minimum required sample size for linear regression models. To ensure accurate prediction in subsequent study participants, we will need 100 individuals to include 10 predictors in our statistical model (50).

Based on the above calculations, we aim to recruit a minimum of **120** patients into this study over 6 months with a minimum of 30 patients in each of the four frailty categories vulnerable, mild, moderate, and severe/very severe. We will continue to recruit patients from the ambulatory clinic until the minimum targets are met.

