5.5 Data collection methods

5.5.1 *Patient Self-Assessed Frailty*: Patients will use the CFS to self-assess frailty at their clinical baseline, which measures nine distinct degrees of frailty from ‘managing well’ to ‘terminally ill’ (**Figure 1**). The wording in the CFS has been adapted and validated for patient-use (32).

5.5.2 *Patient Expectations of Health Care*: Patients will review and rank items on a standardized list of care interventions (i.e. pulmonary exercise programs, homecare, self-management education). The study team developed the list based on services recommended in Health Quality Ontario’s updated ‘Quality Standards for COPD’ document (38), and currently available community-based programs to help individuals with their functional, social, and lung health needs. The document will be written in lay language and a member of the research team will ensure items on the list are well understood by patient participants. Patient participants will rank each item on a likert scale from 1 (least important), to 5 (most important), to indicate their care preferences. ([COPD & Frailty - Baseline survey](#))

5.5.3 *Patient Baseline Health Data* (see **Data Collection Sheet – Baseline visit)**: We will collect variables from direct patient assessment and review of the electronic medical record at the time of recruitment:

- Socio-Demographic Data (age, sex, body mass index, physician-assessed clinical frailty scale score, current dwelling, caregiver support, marital status, education level, type of home assistance services, and duration of time since initial diagnosis).

- COPD-Specific Factors (Spirometry values (FEV1, FVC, FEV1/FVC), smoking history in pack-years, home-oxygen use, 6-minute walk test distance (if available), influenza and pneumococcal vaccination status, use of pulmonary rehabilitation, and number of flare-ups in the last year).
- General Health Data (co-morbidities, presence of family physician).
- Previous Health Service Utilization (hospitalizations, intensive care unit admissions, emergency room visits in last 1-year).

5.5.4 **Physician Data Collection:** We will ask the referring respirologist (in the patient's circle of care) to provide a frailty measurement at the time of study enrolment, using the CFS (Figure 1). This physician will also rank their desired care interventions for the patient using the same standardized list given to study participants (see [Recruitment Survey](#)).

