5.7.1 ***Quantitative Analysis (Objective 1):*** The primary outcome (HRQOL using SGRQ-C scores) will be analyzed using multiple variable linear regression, with degree of frailty as the main predictor ('vulnerable', 'mildly frail', 'moderately frail', and 'severely/very severely frail'). Secondary outcomes for symptom burden (CAT and mMRC scales) and psycho-social wellbeing (GAD-7 and PHQ-9) will be described with median (IQR) statistics within each degree of frailty and analyzed with multiple variable linear regression to determine their associations with progressive degrees of frailty. Finally, the association between frailty and health service utilization (hospitalization, emergency room visit) and mortality will be analyzed with multivariable logistic regression. Potential confounding variables will be selected a-priori and forced into the model, regardless of statistical significance. Backwards selection will be used to obtain the most parsimonious model.

5.7.2 ***Quantitative Analysis (Objective 2):*** We will use descriptive statistics (proportions, means \pm SD, medians (IQR)) to characterize the ranked care expectations, socio-demographic, and disease-specific, variables. Variables will be stratified by physician-assessed degrees of frailty, and chi-square and ANOVA testing will be used to analyze differences in variables across degrees of frailty, for categorical and continuous variables, respectively.

5.7.3 ***Quantitative Analysis (Objective 3 & 4):*** We will calculate the percentage of agreement to assess inter-rater agreement between patients' self-assessed and physician-assessed frailty ratings at the baseline visit. This will be presented as a

cross-tabulation table. We will graph the trajectory of frailty rating between baseline, 6-month, and 12-month visits for the study cohort.

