5.8 Data sources

- **Patient surveys:** For each study visit, patients will be asked to complete surveys relating to: CFS, SGRQ-C, mMRC Dyspnea Scale, CAT, GAD-7 and PHQ-9 .
- **Physician surveys:** CFS and care expectations for patient at time of enrolment
- **Electronic Medical Record:** Baseline health data, socio-demographic data, COPD-specific data, previous health care service utilization (1 year prior to study enrolment)
- **Baseline telephone visit with research team:** baseline health data, COPD specific data, previous health care service utilization.
- **6 & 12 month telephone visits with research team:** CFS, change in health status (stress event or falls) since last visit.

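### No masking is specified between the physician's CFS and care ratings and the staff who take some patients through their own ratings by telephone, so the two may not be independent

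*Combined protocol and SAP*

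**What the plan says.** Section 5.3 (Study flow) sets the order of events. At the clinic visit the physician rates the patient on the CFS and is to "include the frailty rating and their care expectations for the patient in a form". Then: "This form would be automatically available to the research team, which would allow them to contact the patient to obtain verbal consent". The consent call and the telephone baseline visit follow.

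The patient's baseline survey is e-mailed before that visit. The fallback for patients who have not filled it in is: "Baseline Survey was not completed, the study team will go through the questions with the patient". Section 5.8 shows that the CFS is part of what is asked: "patients will be asked to complete surveys relating to: CFS, SGRQ-C, mMRC Dyspnea Scale, CAT, GAD-7 and PHQ-9". Section 5.5.2 places the 1-5 care rankings in the baseline survey and adds that "a member of the research team will ensure items on the list are well understood by patient participants".

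Section 5.5.3, which points to the Baseline Visit data collection sheet, includes "physician-assessed clinical frailty scale score" among its variables.

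For Objective 3, section 5.7.3 plans: "We will calculate the percentage of agreement to assess inter-rater agreement", comparing patient and physician ratings at baseline, with a cross-tabulation. Objective 2 (section 3.0) describes how patients and physicians differ in their care expectations.

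**The concern.** An agreement statistic is informative only if each rater answers without the other's answer in play. Here the physician's rating exists first and is held by the team that may later help the patient choose a CFS level. An interviewer who knows the physician's level can steer the patient towards it without meaning to, through emphasis, prompting or the way an uncertain answer is resolved. The physician's rating precedes the patient's survey answer, so by this route only the patient's rating can move.

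Discordance between patient and physician is part of the study's rationale (section 2.0) and one of its promised results (section 9.0, item d). Anchoring on the physician's rating would hide some of it. The same mechanism could narrow the gap in care rankings under Objective 2. Exposure would also differ within the cohort, since patients who answer online choose their CFS level without an interviewer.

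**Working it through.** **1. The data flow.**

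| Step | Where | What it establishes |
|---|---|---|
| Physician records CFS and care expectations | 5.3, 5.5.4 | Physician's ratings exist before the patient's survey answers |
| Form goes automatically to the research team | 5.3 | Team has access before the consent call |
| Physician CFS listed with baseline-visit variables | 5.5.3 | The rating may also be on the sheet used for the call |
| Team goes through an uncompleted survey by telephone | 5.3 | Same team elicits the patient's answers |
| Survey includes CFS and care rankings | 5.8, 5.5.2 | Both paired measures are exposed |
| Access held back until the patient's answers are locked | nowhere | Not specified; section 7.0 covers confidentiality only |
| Completion mode recorded or analysed | nowhere | Not specified |

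Only the CFS pair feeds Objective 3. The care rankings belong to Objective 2. The item explanation in 5.5.2 is not limited to telephone patients, so the rankings may be exposed somewhat more widely than the CFS.

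**2. Is there a figure in the plan to reproduce?** Not for this point. The plan gives no expected agreement, precision or sample size for Objective 3. The calculated sample sizes in Appendix 1 (84 and 64) concern the Objective 1 regression. They reproduce exactly, and nothing here depends on them.

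**3. Illustration of size. All three inputs are assumptions; none is in the documents.**

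- True agreement: a = 0.45
- Share completing by telephone: f = 0.40 (range 0.20 to 0.60)
- Share of their otherwise discordant ratings that move to the physician's level: s = 0.20 (range 0.10 to 0.30)

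Observed agreement = a + (1 − a) × f × s

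- Central: 0.45 + 0.55 × 0.40 × 0.20 = 0.494, a shift of 4.4 points
- Low: 0.45 + 0.55 × 0.20 × 0.10 = 0.461, a shift of 1.1 points
- High: 0.45 + 0.55 × 0.60 × 0.30 = 0.549, a shift of 9.9 points

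Telephone completers alone: 0.45 + 0.55 × 0.20 = 0.56 (0.505 at s = 0.10; 0.615 at s = 0.30).

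Over a wider grid (a from 0.4 to 0.7, f from 0.10 to 0.75, s from 0.1 to 0.3) the shift runs from 0.3 × 0.10 × 0.1 = 0.3 points to 0.6 × 0.75 × 0.3 = 13.5 points.

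**4. Against sampling error.** With the planned 120 patients the 95% half-width at 45% agreement is 1.96 × √(0.45 × 0.55 / 120) = 8.9 points. The central shift is about half of that. For telephone completers alone, 0.40 × 120 = 48 patients, the half-width is 1.96 × √(0.45 × 0.55 / 48) = 14.1 points, against an assumed shift of 11 points.

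**5. Could the data reveal it afterwards?** Hardly. A comparison of agreement by mode, 60% against 50%, has about 15% power with 30 and 90 patients and about 19% with 60 and 60. If mode is related to frailty, a difference would also be confounded.

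**The case against.** The strongest reply is that availability is not exposure. The plan says that the form reaches the team. It does not say that the person making the call opens it or has the rating on screen. The Recruitment Survey and the Baseline Visit sheet are linked forms whose layout and permissions cannot be read from the text. This stands. A reader might infer that the interviewer sees the physician's rating while helping the patient; the documents support only that nothing prevents it.

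Second, self-completion online is the default and telephone the fallback. Patients use CFS wording adapted for them (5.5.1), and section 8.3 commits staff to neutral language. These features limit the risk. The language rule addresses stigma, however, and is not masking.

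Third, the illustration assumes its own direction. It moves every shifted rating exactly onto the physician's level, whereas partial movement on a nine-level scale would leave exact agreement unchanged. This stands too: inflation is plausible, not established.

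Fourth, Objective 2 is analysed descriptively and across frailty levels (5.7.2), with no formal patient-physician test, and 5.5.2 concerns understanding the items rather than choosing a rank. The consequence there is weaker than for Objective 3.

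That the likely shift is smaller than the sampling error bears on priority but does not remove the point. A bias of this kind moves the estimate, and the confidence interval does not reflect it.

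**Conclusion.** The point holds in a limited form. The described workflow permits the patient's CFS, when taken by telephone, to be elicited by someone with access to the physician's rating, and no safeguard is specified. Percent agreement for Objective 3 could plausibly be inflated, and the gap in care rankings for Objective 2 could shrink. Online completers are largely protected for the CFS.

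The size is unknown. Under the assumed inputs it is a few percentage points, and it reaches the sampling error only if telephone completion is common and anchoring strong.

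Three stronger readings are not supported:

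- **That agreement will be inflated.** Neither the caller's exposure nor the direction of any effect is documented.
- **That the bias grows with frailty because frailer patients use the telephone more.** No passage gives completion mode by frailty.
- **That the primary analysis is compromised because the SGRQ-C is in the same survey.** Nothing in the documents shows this.

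The change is worth making because it costs little and the effect could not be reliably detected afterwards.

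**What to change.** In sections 5.3 and 5.5.3:

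1. Release only the screen ID and contact permission from the Recruitment Survey to the person who makes the consent call and the baseline call. Hide the physician's CFS and care-ranking fields until the patient's baseline survey is locked.
2. Do not carry the physician CFS on the Baseline Visit sheet. Merge it from the Recruitment Survey at analysis.
3. Record completion mode (online or telephone) for each survey. Report agreement by mode as description only, not as a test for leakage.

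If the caller is already masked in practice, one sentence in 5.3 saying so settles the first item. If baseline collection is finished, report who had access to the physician's ratings and, where mode can be recovered, agreement by mode.

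Cost: a change in form access, one field moved off a sheet and one added variable. It should need no extra visits or sample size and probably no extra staff, although the form platform is not described and this needs confirming. The small downside is that the caller cannot see progress towards the minimum of 30 patients per frailty category (5.4); another team member can track it.
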